### RATIONALE

CCR FAST Protocol has been amended to account for the COVID-19 pandemic, which has resulted in increased health and safety concerns for study participants, their caregivers, and clinical site staff because of the risks of person-to-person transmission of disease.

Because of anticipated disruptions in follow-up visits associated with the global COVID-19 pandemic, the 6 month visit has been amended. Recently care delivery has initiated in-person visits within HealthPartners and Cardiac Rehabilitation in-person appointments have resumed. The final 8 study subjects will be completing the 6 month study visit in May/June timeline will have the following:

**Specific data points in the protocol, along with a rationale for each change, are summarized below:**

- Complete Cardiac Rehabilitation Visits ***–in-person visits conducted in align with care delivery.***
- 6 Month Final Visit – ***conduct by phone or video visit.***
- Quality of Life, Mood and Cognitive Functioning Questionnaires ***-Questionnaires that can be obtained by phone or video visit.***
- Blood Test ***–Obtain historical results from medical records so not to require an additional in-person visit.***
- 24 Hour Ambulatory Blood Pressure ***–Not obtained so not to require additional in-person visits. During all Cardiac Rehabilitation visits blood pressure, heart rate are being monitor.***
- Brain MRI (Magnetic Resonance Imaging) – ***To be obtained at Neuroscience Center Imaging Department --this is the Primary Endpoint for the study.***

## PROTOCOL SYNOPSIS

PROTOCOL TITLE	Comprehensive Cardiac Rehabilitation Feasibility After Stroke
SHORT TITLE	CCR FAST
STUDY PHASE	Enrollment Complete
STUDY OBJECTIVES AND PURPOSE	

Study Purpose
 
The purpose of this study is to demonstrate the feasibility and safety of including stroke patients in a comprehensive cardiac rehabilitation (CCR) program, while examining the clinical value in reducing stroke recurrence, myocardial infarction, readmission, and mortality in stroke patients.
	

Primary Objective
 
 
• To assess the feasibility of comprehensive cardiac rehabilitation for stroke patients.
 
	

Secondary Objective (s)
 
 
• To explore the potential benefits of cardiac rehabilitation for stroke patients by describing the 6-month rates of recurrent stroke, myocardial infarction, hospital readmission for a cardiovascular or cerebrovascular indication, silent stroke on MRI and death.
 
	

STUDY DESIGN
	
Study Type	Feasibility
Study Indication Type	Intervention
Study Design	
This study is a prospective feasibility study, which will consist of a single arm of ischemic stroke patients. Seventeen patients will be consented through rolling recruitment to participate in a 36-session CCR program over 12-week period at Regions Hospital Outpatient Cardiac Rehabilitation facility. Participants will join the existing cardiac rehabilitation program, and undergo the same types of exercise therapy and education as the cardiac patients, with slight modifications to the educational material to include brain pathology. The primary endpoint of the study is the successful completion of the study protocol, which consists of attending 75% of the CCR sessions, completing brain MRI and laboratory tests at the end of the study, and attending the end of study visit.
 
Baseline data will be collected while patients are admitted at Regions Hospital. If patients need more time to recover, baseline visits will take place at HealthPartners Neuroscience Center within 3 months from the time of stroke. CCR sessions will also begin within 3 months after the patient's admission for ischemic stroke. The research staff will conduct a 6-week phone call (6-weeks after beginning CCR) to determine if any adverse events (AE) or serious adverse events (SAE) have occurred and to obtain an updated medication list. The 3-month and 6-month clinic visits will take place at the Neuroscience Center and will be 3 months and 6 months from the date of the baseline visit. Patients will meet with [name] and the research staff. The patients' vitals will be

	
taken and standard assessments (described below) will be performed, which are typically performed as standard of care. The 6-month clinic visit will also include laboratory tests and a MRI. 24-hour ambulatory blood pressure will be monitored and recorded at baseline and at 6-months. The chart below includes the visit schedule and data collection information.
			
Planned Duration of Subject Participation	
The duration of study participation for each subject is anticipated to be 6 months from baseline.
			
OUTCOMES	Primary-Completion rate	
 
CCR sessions
 
6-month study visit, MRI and labs
 
		
	Secondary-Benefit	
 
6-month rates of recurrent stroke, myocardial infarction, hospital readmission for a cardiovascular or cerebrovascular indication, silent stroke on MRI and death.
 
Beginning and end comparison of weight, BMI, blood pressure, and laboratory values
 
		
SUBJECT SELECTION				
Targeted Accrual	
For this study, we will enroll 17 eligible ischemic stroke patients. We will continue to recruit patients until the 17th patient is enrolled in CCR.
			

Inclusion Criteria
 
 
Age <math>\geq</math> 18 years
 
Patient has suffered an ischemic stroke
 
Patient should be ambulatory (non-disabling stroke) to be able to participate in the CCR exercise program
 
Patient is able to start cardiac rehabilitation within 3 months of stroke
 
				

Exclusion Criteria
 
 
No baseline (index admission for ischemic stroke) MRI completed
 
Life expectancy < 1-year
 
Presence of brain hemorrhage: intracerebral hemorrhage, subarachnoid hemorrhage, subdural hematoma, or epidural hematoma
 
Concurrent diagnosis of seizure disorder
 
Patient with moderate or severe neurologic deficits, limiting their ability to participate in the CCR exercise program
 
Cardiopulmonary conditions preventing the patient from participation, such as severe heart failure, severe aortic stenosis, and exercise-induced asthma
 
Patient with cognitive dysfunction impairing their ability to follow directions
 
Anticipated procedures such as carotid stenting, carotid endarterectomy, and intracranial aneurysm coiling
 
Patient unable to commit to the frequent visits of the CCR program
 
Participation in other interventional research (observational research is allowed)
 
Unable to have brain MRI
 
Non-English speaker
 
Pregnant women
 
				

## 1. INTRODUCTION

There is a significant overlap in risk factors (e.g. hyperlipidemia, hypertension, smoking, diabetes, obesity, and a sedentary lifestyle) between ischemic stroke and coronary artery disease. These risk factors contribute to the development and progression of atherosclerosis, which is a major cause of ischemic stroke and coronary artery disease. This is why prevention strategies for coronary artery disease and stroke are similar.

Comprehensive cardiac rehabilitation (CCR) is standard-of-care after myocardial infarction, which includes aerobic exercise, education/counseling, and medication compliance oversight. CCR has been shown to improve vascular risk factor control and survival rates, as well as reduce re-infarction and hospital readmission rates. CCR has become an integral part of care for many cardiac and pulmonary diseases and is reimbursable by insurance companies. As for stroke, only a few studies have examined the use of CCR and these studies focused on assessing the impact of the program on risk factors control such as cholesterol level, blood pressure, and exercise endurance. No studies examined the impact of CCR on clinical endpoint in stroke patients, such as stroke recurrence, readmission, occurrence of other vascular events, and death. Due to this lack of evidence, CCR is not reimbursable for a stroke diagnosis.

The standard of care after stroke, revolves around restoring the functions lost by stroke through engaging in physical, occupational, and speech therapies. This is a fundamental philosophical difference between CCR and stroke rehabilitation. The former aims to improve wellness and bring the patient to a healthier state compared to baseline, while the latter aims to bring the patient back to baseline. Another important difference between CCR and stroke rehabilitation is the extent and intensity of patient education; while there is an education curriculum for CCR, stroke patients' education typically involves a discussion with providers during hospitalization or clinic visits counsel regarding risk factors. Coaching provided by the CCR program (e.g. helping patients implement a healthier lifestyle and ensuring medication compliance) is lacking in post-stroke care.

A few studies have attempted to integrate CCR after stroke. These studies showed that CCR has short-term beneficial effect on vascular risk factors control (blood pressure, lipid profile, body mass index) and exercise endurance. However, none of these studies specifically evaluated the effect that CCR has on clinical endpoints such as stroke recurrence and hospital readmission.

The overall goal of this study is to assess the feasibility of stroke patient participation in Regions Hospital's CCR program. Our study will examine the ability of stroke patient to complete the current CCR program (provided as standard of care by cardiology department). The program consists of 3 sessions per week over 12 weeks. Exploratory endpoints will be the event rate of recurrent stroke at 6 months, MI, death, hospital readmission for a cardiovascular or cerebrovascular indication, and silent stroke on MRI. These analyses will help us with our future power analysis for a subsequent larger trial. The experience, workflow, and the knowledge gained from this study will be used to design a larger study, comparing CCR with conventional post-stroke treatment.

## **2. SUMMARY OF INTERVENTION DESCRIPTION**

For the study intervention, all patients will be prescribed 36 sessions of comprehensive cardiac rehabilitation, which will occur over 12 weeks. Participants will attend the standard of care ongoing cardiac rehabilitation sessions at Regions Hospital Outpatient Cardiac Rehabilitation facility at [name]. The cardiac rehabilitation program is staffed by exercise physiologists, registered dieticians, and registered nurses, under the direction of a cardiologist. The cardiac rehabilitation program includes supervised exercise, nutritional counseling, medication review, and patient education. Stroke patients will receive the same education sessions as the cardiac patients, except for three sessions. Because there were three sessions that were specific to cardiac patients (and therefore not relevant to stroke patients), these sessions will be replaced with three stroke specific education sessions, which were developed by [name].

Each session will last approximately 60-90 minutes, and include 30-40 minutes of aerobic exercise, 15 minutes of strength training, and a 30 minutes group education session. Patients will be instructed to exercise at a rate of perceived exertion of 11-13 on the Borg scale, corresponding to “fairly light” to “somewhat hard”. Exercise intensity will be increased 0.5-1 metabolic equivalent every 1-3 weeks according to patient exercise training parameters. There are 16 educational modules that will be presented to the patients at the group education sessions. The educational material will be modified to include brain pathology.

At the initial CCR visit, an ambulatory blood pressure monitor will be placed on and sent home with the patient. The patient will be monitored for 24 hours and asked to return to the outpatient cardiac rehabilitation facility the next day to return the monitor.

If a patient drops out of the study or stops attending CCR classes, the research staff will call the patient to ask why he or she stopped attending CCR. If the research staff is unable to reach the patient after two phone call attempts, they will attempt to reach the patient at his or her next Neuroscience Center clinic visit to obtain a drop out reason. In addition, adverse or serious adverse events will be monitored by the study staff throughout the study.

## **3. OBJECTIVES**

### **3.1. Primary Objectives**

To assess the feasibility of comprehensive cardiac rehabilitation for stroke patients.

### **3.2. Secondary Objectives**

To explore the potential benefits of cardiac rehabilitation for stroke patients by describing the 6-month rates of recurrent stroke, myocardial infarction, hospital readmission for cardiovascular or cerebrovascular indication, silent stroke on MRI and death.

## 4. STUDY DESIGN

This study is a prospective feasibility study, which will consist of a single arm of ischemic stroke patients. Seventeen patients will be consented through rolling recruitment to participate in a 36-session CCR program over 12-week period at Regions Hospital Outpatient Cardiac Rehabilitation facility. Participants will join the existing cardiac rehabilitation program, and undergo the same types of exercise therapy and education as the cardiac patients, with slight modifications to the educational material to include brain pathology. The primary endpoint of the study is the successful completion of the study protocol, which consists of attending 75% of the CCR sessions, completing brain MRI and laboratory tests at the end of the study, and attending the end of study visit.

Baseline data will be collected while patients are admitted at Regions Hospital. If patients need more time to recover, baseline visits will take place at HealthPartners Neuroscience Center within 3 months from the time of stroke. CCR sessions will also begin within 3 months after the patient's admission for ischemic stroke. The research staff will conduct a 6-week phone call (6-weeks after beginning CCR) to determine if any adverse events (AE) or serious adverse events (SAE) have occurred and to obtain and updated medication list. The 3-month and 6-month clinic visits will take place at the Neuroscience Center and will be 3 months and 6 months from the date of the baseline visit. Patients will meet with [name] and the research staff. The patients' vitals will be taken and standard assessments (described below) will be performed, which are typically performed as standard of care. The 6-month clinic visit will also include laboratory tests and a MRI. 24-hour ambulatory blood pressure will be monitored and recorded at baseline and at 6-months. The chart below includes the visit schedule and data collection information.

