## **7.2. Subject Withdrawal**

Subjects may withdraw from study at any time for any reason without penalty or be terminated from the study by the clinical investigator (see provisions for termination by study team.) The investigational team will document the reason(s) for withdrawal. In the event a subject chooses to withdraw from study before Visit 4, the safety procedures described in Section 6.2.4. will be collected within 14 days following subject's decision to withdraw. For all subjects who withdraw, all final safety assessments will be collected regardless of time elapsed since the previous visit. In addition to final visit, subjects who withdraw early will be contacted within 7 days by study staff via telephone to assess for the development of any new and/or ongoing AEs and concomitant medications. Efforts will be made to recruit subjects to replace any withdrawals so as to maintain an n=17.

Subject's participation may be terminated at the discretion of the investigator. Individuals may be withdrawn for the following reasons:

- Clinically significant adverse events
- Lost to follow-up
- Protocol violations
- Inability to tolerate study intervention
- Other

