## **9.4. Secondary Analyses**

For the secondary analyses, we will explore the potential benefits of cardiac rehabilitation for stroke patients by describing the 6-month rates of recurrent stroke, myocardial infarction, hospital readmission for a cardiovascular or cerebrovascular indication, silent stroke on MRI and death. We will assess the individual and composite event rates by calculating the mean and 95% confidence interval. This will provide information to allow us to power a larger study.

Additionally, we plan to descriptively compare weight, BMI, blood pressure, and laboratory values at the beginning and end of the study. We will do this by calculating the mean and 95% confidence intervals for these values.

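### The 17 patients are counted at consent in one place and at CCR enrolment in another, and no denominator is named, so patients who consent but never start CCR can drop out of the completion rate and raise it

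*Combined protocol and SAP*

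**What the plan says.** Three statements fix the number 17, and they do not count the same people.

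- **Section 4, repeated in the synopsis design text:** "Seventeen patients will be consented through rolling recruitment to participate in a 36-session CCR program over 12-week period". The count is taken at consent.
- **Synopsis, Targeted Accrual:** "We will continue to recruit patients until the 17 th patient is enrolled in CCR". The count is taken at entry to CCR, which allows more than 17 consents.
- **Section 7.2:** "Efforts will be made to recruit subjects to replace any withdrawals so as to maintain an n=17". The count is topped up when someone leaves.

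Section 8.2.2 makes a person a study participant at consent. Consent belongs to Visit 1 (Section 6.2.1), which normally takes place during the stroke admission and can be deferred for recovery. Section 4 then allows a delay before the programme: "CCR sessions will also begin within 3 months after the patient's admission for ischemic stroke".

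Section 9.3 defines completion by 75% attendance, the 6-month MRI and laboratory tests, and the end-of-study visit. It gives no denominator. It does promise counts of those who agreed, started, dropped out and completed, with reasons for non-completion. Section 9.4 says "We will assess the individual and composite event rates by calculating the mean and 95% confidence interval", without naming the patients or time zero. Section 9.5 takes 17 from the capacity of the CCR course and computes precision on it.

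**The concern.** Consent can precede the first CCR session by weeks. In that interval a patient may lose interest, fall ill again or die. Under the consent count this patient is one of the 17 and a non-completer. Under the accrual rule, or after replacement under Section 7.2, the same patient need not be among the 17 at all. Followed as written, the rules give different completion rates from the same data, and nothing in Sections 9.3 to 9.5 says which is primary.

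This matters because completion is the primary outcome and feasibility is the primary objective. Consenting and then not starting is itself information about feasibility. If the denominator is chosen once the counts are known, the choice can follow the result. The event rates have the same gap in definition, and Sections 1 and 9.4 intend them to help power a larger study.

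**Working it through.** **1. The plan's own figure.** Inputs from Section 9.5: n = 17, completion 75%, 95% confidence, half-width 20.2%. The Wald half-width is 1.96 × √[p(1−p)/n].

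- p = 0.75, n = 17: 20.58%.
- p = 13/17 = 0.7647, the attainable proportion nearest 75%: 20.16%, which rounds to the stated 20.2%.

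So the figure matches 13 completers out of a full denominator of 17, with no allowance for consented patients outside it.

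**2. Completion on all consented patients.** Hold 13 completers fixed and add k never-starters who sit outside the 17. The documents give no value for k, so these are assumptions. Rate = 13/(17 + k).

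| k | Rate | Wald half-width | Exact (Clopper-Pearson) 95% CI |
|---|---|---|---|
| 0 | 13/17 = 76.5% | 20.2% | 50.1% to 93.2% |
| 1 | 13/18 = 72.2% | 20.7% | 46.5% to 90.3% |
| 3 | 13/20 = 65.0% | 20.9% | 40.8% to 84.6% |
| 5 | 13/22 = 59.1% | 20.5% | 36.4% to 79.3% |

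Leaving out 1 to 5 never-starters raises the reported rate by about 4 to 17 percentage points. A never-starter adds one to the denominator and nothing to the numerator, so the direction is fixed whenever at least one patient completes. The half-width hardly moves, so the interval gives no sign of the shift.

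**3. Event rates.** Here the direction is not fixed. Suppose 2 events among 17 starters (11.8%) and 3 never-starters left out, both assumed. Rate on all 20 = (2 + e)/20, where e is the number of never-starters with an event:

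- e = 0: 10.0%, so omission raised the rate.
- e = 1, 2 or 3: 15.0%, 20.0% or 25.0%, so omission lowered it.

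**4. The clock.** Section 4 times the 3- and 6-month visits from the baseline visit. Sections 6.2.2 and 6.2.3 schedule them from the start of cardiac rehabilitation. Time between baseline and the first session is therefore inside the 6 months on one reading and outside it on the other.

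**The case against.** **The promised flow counts let a reader recompute completion.** This is largely true, and it limits the harm: completers can be divided by those who agreed. It does not settle in advance which rate is primary, and it does not help with event rates.

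**Being enrolled in CCR may mean registered rather than having attended.** That would narrow the gap between the two counts without closing it.

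**The study asks whether patients can complete the programme, so starters are a legitimate denominator.** Section 1 does speak of the ability to complete it, so a rate among starters is worth reporting. It does not reconcile the conflicting counts of 17.

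**Never-starters are a separate matter from replacement.** A reader might infer this, but Section 7.2 covers any withdrawal and Section 8.2.2 makes patients participants at consent. Someone who withdraws before the first session falls under the replacement rule, so the two issues overlap and should be settled together.

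**The event rates must be biased downward by immortal time.** A reader might also infer this. With a constant hazard and a true 6-month risk of 10%, λ = −ln(0.90)/6 = 0.01756 per month. Counting from baseline, 1 − exp[−λ(6 − s)] gives 8.4%, 6.8% or 5.1% for a CCR start at s = 1, 2 or 3 months. That is the extreme case under constant hazard, because it needs every earlier event to prevent starting. Silent stroke read on the 6-month MRI cannot do so, and a readmission or minor stroke need not. If half the hazard were disqualifying (an assumption), 1 − exp[−λ(6 − s/2)] gives 9.2%, 8.4% or 7.6%. Counted from CCR start, there is no such waiting time. A deferred baseline visit also shortens the gap.

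**Conclusion.** The conflict over who the 17 are is real, and it bears on the primary outcome. If any consented patient who never started is left out, completion is overstated. The overstatement is about 4, 11 or 17 points for 1, 3 or 5 such patients, given 13 completers. The direction needs no assumption beyond at least one completer; the size rests on assumed counts.

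The documents do not support a general claim that event rates are understated. That depends on which clock is used, on whether early events keep patients from starting, and on whether never-starters had events at all. If they had none, leaving them out raises the rate. What does stand for Section 9.4 is that the patient set is unnamed and the two clocks disagree.

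The synopsis lists enrolment as complete, but the amendment rationale shows the last 8 patients' 6-month visits still to come. The correction concerns the analysis set and does not require any change to recruitment.

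**What to change.** 1. Reconcile the synopsis design text, the synopsis accrual target, Section 4 and Section 7.2 so that 17 has one meaning.
2. In Section 9.3, state that the primary completion rate uses all consented eligible patients, with never-starters and replaced withdrawals counted as non-completers. Give the rate among CCR starters as supportive, and define a starter.
3. In Section 9.5, say that the ±20.2% assumes a denominator of 17 and will be recomputed for the number actually consented.
4. In Section 9.4, name the patient set and reconcile the 6-month clock between Section 4 and Sections 6.2.2 and 6.2.3. Include events already recorded from consent onward in never-starters, and report how complete their follow-up is.

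Items 1 to 3 cost only wording, since Section 9.3 already collects the counts. Item 4 has a limit: adverse-event recording stops at withdrawal (Section 8.2.2), final procedures fall within 14 days of the decision to withdraw (Section 7.2), and there is no imputation (Section 9.2). Full 6-month event and MRI data on never-starters are therefore not assured and should not be implied. The main downside is a possibly lower headline completion rate.

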#### **6.2.4. Visit 4: 6-Month MRI and Clinic Visit**

- Undergo MRI.
- Collect laboratory samples; lipid panel, basic metabolic panel, coagulation panel, glycosylated hemoglobin, and Cotinine.
- Collect vital signs.
- Review current medications.
- Administer MoCA.
- Complete EQ-5D.
- Complete PHQ-9.
- Obtain NIHSS score with physician.
- Obtain MRS score with physician.
- Record AEs/SAEs.

\*This visit may be separated into 2 visits, if needed.

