#### **6.5. Vital Signs**

Vital signs and O2 saturation will be recorded at visits 1, 3, and 4 and recorded prior to the MRI and blood draw. For within subject consistency, brachial artery pressure will be obtained in the routine fashion and the same arm will be used for all study measurements.

Blood pressure and heart rate will be measured after subject has been sitting quietly for a minimum of 5 minutes. Vitals signs and O2 saturation will be monitored by clinical staff during each visit of the study.

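### Section 9.4 compares one undefined blood pressure, although two different measurements are collected and the 6-month ambulatory reading is dropped for the final 8 subjects

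*Combined protocol and SAP*

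**What the plan says.** **Outcome and analysis.** The synopsis lists as a secondary outcome "Beginning and end comparison of weight, BMI, blood pressure, and laboratory values". Section 9.4 states that "we plan to descriptively compare weight, BMI, blood pressure, and laboratory values at the beginning and end of the study", using the mean and 95% confidence interval of the values. Neither place names a type of measurement, a starting reading or a pairing rule. Section 9.2 rules out imputation.

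**Seated cuff pressure.** Section 6.5 specifies: "Blood pressure and heart rate will be measured after subject has been sitting quietly for a minimum of 5 minutes". Together with oxygen saturation, vital signs "saturation will be recorded at visits 1, 3, and 4 and recorded prior to the MRI and blood draw". Visit 1 takes place during the stroke admission where possible, otherwise in clinic within 3 months of the stroke (Section 4).

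**24-hour ambulatory pressure.** Section 4 and the synopsis both say "24-hour ambulatory blood pressure will be monitored and recorded at baseline and at 6-months". Section 2 places the first recording elsewhere: "At the initial CCR visit, an ambulatory blood pressure monitor will be placed on and sent home with the patient". Under Section 4, rehabilitation may begin up to 3 months after admission. The visit 4 list in Section 6.2.4 has "Collect vital signs" and no ambulatory item.

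**Final 8 subjects.** The COVID-19 amendment at the front of the protocol makes their 6-month visit a phone or video contact. It states that the 24-hour recording is not obtained, and adds: "During all Cardiac Rehabilitation visits blood pressure, heart rate are being monitor". The MRI remains in person.

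**The concern.** A 24-hour mean, a seated reading and a reading taken during a rehabilitation session are different quantities, so a beginning-to-end change means something only within one type. Section 9.4 leaves the type open. The choice would therefore be made at analysis, when the data can be seen.

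Two things are at stake.

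- **Who is compared.** If the beginning mean uses everyone with a first reading and the end mean uses everyone with a last reading, the two means come from different patients once the final 8 lack a 6-month value. A difference between those groups at the start would then look like a change over the programme.
- **What is compared.** If another type of reading stands in for the missing 6-month value, the difference between methods enters the change. In a single-arm study there is no control group in which it would cancel.

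The starting point matters as well. A seated pressure from visit 1 can date from the acute admission, so its change can include whatever happened before rehabilitation began. The first ambulatory reading may be weeks or months later if Section 2 is followed.

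**Working it through.** **The plan's own figure.** The documents give no figure for blood pressure. The only design figure is the half-width of 20.2 percentage points for the completion rate (Section 9.5). It reproduces as 1.96 × √(p(1−p)/17) = 20.16% at p = 13/17, and is 20.58% at exactly 75%. The present point does not depend on it.

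**Step 1: available pairs.**

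| Measurement | First reading | 6-month reading, before amendment | 6-month reading, final 8 |
|---|---|---|---|
| Ambulatory | baseline (Section 4, synopsis) or initial rehabilitation visit (Section 2) | required by Section 4; not in the Section 6.2.4 list | not obtained |
| Seated cuff | visit 1 | visit 4 | not assured: phone or video visit |

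If the 8 are among the 17, ambulatory pairs number at most 17 − 8 = 9. For seated pressure the limit is less certain. Section 6.5 ties vital signs to the time before the MRI, which these subjects still attend, but the amendment mentions no pressure reading there.

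**Step 2: separate means over different patients.** Let a be the starting mean in the 9 patients with an end reading and b the starting mean in the 8 without one. The end mean (9 patients) minus the beginning mean (17 patients) equals

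mean change in the 9 + [a − (9a + 8b)/17] = mean change in the 9 + (8/17)(a − b).

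Since 8/17 = 0.47, each 1 mmHg by which the two groups differ at the start adds 0.47 mmHg to the apparent change. The documents give no value for a − b.

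**Step 3: substituting another type of reading.** Assume a systematic difference d between session and ambulatory systolic pressure of 5 to 10 mmHg; this is not in the documents. If 8 of 17 patients have an ambulatory start and a session end, the mean change shifts by (8/17) × d:

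- d = 5: 2.4 mmHg
- d = 10: 4.7 mmHg

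**Step 4: precision of a like-for-like analysis.** The 95% half-width of a mean within-patient change, in units of the SD of the change, is t(0.975, n−1)/√n:

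- n = 17: 0.51 SD
- n = 9: 0.77 SD

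The ratio is 0.77/0.51 = 1.5, so the interval is about half as wide again.

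**The case against.** The strongest reply is that each measurement has its own planned pair: seated pressure at visits 1 and 4, ambulatory pressure at baseline and 6 months. No section substitutes one for the other. The amendment says the ambulatory value is not obtained and does not name session readings as the 6-month value. With no imputation, the natural reading is that the value stays missing. This stands. A reader might infer that mixing is planned or likely for the final 8; the text shows only that it is possible and not excluded.

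A reader might also infer from Section 6.2.4 that no patient has a 6-month ambulatory value. The documents do not support that. Section 4 and the synopsis require the reading, and the visit chart they refer to, which is not in the text available here, may list it. Nor is there a basis for supposing that all 17 patients would have mismatched readings: those before the amendment had an in-person visit 4 with vital signs. The final 8 are not left with session readings alone, since the seated reading at 3 months is unchanged.

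Section 2 can be read as the operational detail of the baseline in Section 4, which would also explain why the visit 1 list has no monitor. That is reasonable, but the text does not say so.

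Finally, blood pressure is not part of the stated secondary objective, which concerns clinical events, and its comparison is descriptive. That limits the weight of the point. It does not say which pressure Section 9.4 means or which patients enter each mean.

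**Conclusion.** The point holds as a gap in the analysis definition. Two measurements that are not interchangeable are collected, neither is designated as the outcome, and the start of one is described in two ways. Followed as written without imputation, the ambulatory comparison sets a beginning mean on up to 17 patients against an end mean on at most 9. This rests on the final 8 being among the 17. The seated comparison may be limited in the same way.

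The size of any distortion cannot be fixed from the documents. The 2.4 to 4.7 mmHg figure depends wholly on the assumed 5 to 10 mmHg method difference and on session readings actually being used as end values. The mismatch between patient sets in separate means needs neither assumption, although its effect depends on how the two groups differed at the start.

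The change is worth making because it costs little. It does not touch the primary endpoint or the sample size.

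**What to change.** In Section 9.4, replace the single blood pressure with two outcomes reported separately:

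1. change in 24-hour ambulatory pressure;
2. change in seated cuff pressure measured as Section 6.5 describes.

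For each, give the mean within-patient change with a 95% confidence interval, in patients who have both readings of that type, and state n and the actual times of the first and last readings. State that rehabilitation-session readings are not used as the 6-month value for either outcome.

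Reconcile the synopsis and Section 4 with Section 2 on when the first ambulatory recording is taken. Reconcile Section 6.2.4 with Section 4 and the amendment, so that the text says once which subjects were to have a 6-month recording. This should not become a new procedure: enrolment is complete, and a general requirement added to Section 6.2.4 would gain little and would conflict with the amendment.

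The cost is wording only, with no new data collection. The downside is precision: both comparisons may rest on about 9 patients, with a half-width of about 0.77 SD of the change instead of 0.51 SD with 17 pairs.
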